3.1.2 Exclusion Criteria

3.1.2.1 Patients who have HIV or hepatitis C. Patients would not be excluded for hepatitis B surface antigen positivity if on Lamivudine.

3.1.2.2 Patients receiving coumadin.

3.1.2.3 Patients with a left ventricular ejection fraction of $<$ 45%.

3.1.2.4 Patients with a DLCO $<$ 55% of normal or an FEV1 $<$ 60% of normal, based on either NIH or USA normal ranges.

3.1.2.5 Patients who have an active 2nd malignancy requiring systemic treatment.

3.2 RESEARCH ELIGIBILITY EVALUATION

- A blood sample will be submitted to the NIH pathology department for analysis of CD25 expression (an eligibility criterion) by FACS analysis. This analysis will be done in the Laboratory of Pathology, NIH (Anatomic Pathology Dept., CC), a College of American Pathologists (CAP) and CLIA-approved laboratory, by standardized diagnostic techniques.
- Complete history and physical examination with documentation of measurable disease (lymph nodes, spleen, liver), stage, and performance status within 2 weeks before starting LMB-2. Physical examination should record the diameter, in two planes, of the largest palpable nodes in each of the following sites: cervical, axillary, supraclavicular, inguinal, and femoral. Physical examination should record liver and spleen size as determined by measurement below the respective costal margin.

- ECG and CXR within 3 days before starting LMB-2.
- CT scan of the chest, abdomen, and pelvis, or abdominal MRI, within 4 weeks before starting LMB-2.
- Serum anti-LMB-2 antibody assay, HIV, Hepatitis B surface antigen, and hepatitis C screen within 2 months before starting LMB-2.
- Laboratory evaluation within 2 weeks before starting LMB-2 will include CBC/differential, acute care panel (electrolytes, glucose, BUN, creatinine), hepatic panel (AST, ALT, Alkaline phosphatase, total and direct bilirubin), albumin, LDH, PT, Beta 2 microglobulin (B2M), serum protein electrophoresis (SPEP), urinalysis, and a 24 urine creatinine clearance and total protein. A CBC/differential, acute care panel, hepatic panel, and albumin must be done within 3 days of starting cycle 1.
- Urine or serum pregnancy test within 72 hours before starting LMB-2 in women with childbearing potential.
- Bone marrow biopsies and echocardiogram with left ventricular ejection fraction calculation, and stress test, will be done on all patients within 2 months before starting LMB-2.

3.3 INCLUSION OF WOMEN AND MINORITIES

Inclusion of Women and Minorities. No eligible women and minorities will be excluded from the protocol. There is no basis for exclusion of otherwise eligible patients on the basis of age, gender or race.

3.4 RECRUITMENT STRATEGIES

This protocol may be abstracted into a plain language announcement posted on NIH websites and on NIH social media platforms.

3.5 PARTICIPANT REGISTRATION AND STATUS UPDATE PROCEDURES

Registration and status updates (e.g., when a participant is taken off protocol therapy and when a participant is taken off-study) will take place per CCR SOP ADCR-2, CCR Participant Registration & Status Updates found at:

<https://ccrod.cancer.gov/confluence/pages/viewpage.action?pageId=73203825>.

3.5.1 Screen Failures

Screen failures are defined as participants who consent to participate in the clinical trial but are not subsequently assigned to the study intervention or entered in the study. A minimal set of screen failure information is required to ensure transparent reporting of screen failure participants, to meet the Consolidated Standards of Reporting Trials (CONSORT) publishing requirements and to respond to queries from regulatory authorities. Minimal information includes demography, screen failure details, and eligibility criteria.

4 STUDY IMPLEMENTATION

4.1 STUDY DESIGN

This is a Phase II study to test the response of patients with HCL to LMB-2. LMB-2 will be given every 28 days (minimum of 25 days) for up to 6 cycles. No patient whose serum neutralizes > 75% of the activity of 1 µg/mL of LMB-2 will be retreated. In patients who

achieve a CR with minimal residual disease (MRD), defined as positive immunohistochemistry of bone marrow biopsy or flow cytometry of blood, no more than 4 additional cycles of LMB-2 will be administered. Patients with CR without MRD may receive 2 additional cycles. Patients who relapse after >2 months of a CR or PR are eligible for retreatment with LMB-2 alone on the same schedule if they still meet initial eligibility criteria and were not removed from study due to toxicity, provided that the study is still open and the LMB-2 supply permitting. Stopping rules in this case will be the same as those during initial LMB-2 administration. Patients will be treated with LMB-2 as described below. Response and duration of response will be determined as described in section [13](#).

4.2 DRUG ADMINISTRATION

LMB-2 Infusion: 40 µg/Kg will be infused through a peripheral I.V. or central line in 50 ml of 0.9% NaCl and 0.2% albumin via a PAB container over 30 minutes every other day for 3 doses (QOD x 3). Additional IV fluid will be given as described below. The first cycle will be administered on the Oncology Inpatient Unit. If treatment is tolerated well, then subsequent doses can be administered on an outpatient basis.

Premedication: Patients will be medicated with 25 mg hydroxyzine and 150 mg ranitidine orally 1 hour prior to and 8 hours after each dose. Acetaminophen 650 mg P.O. will be given every 6 hours for 4 doses starting 1 hour prior to each LMB-2 dose. Dexamethasone 20 mg i.v. will be given 2 hours prior the 1st dose of each retreatment cycle. While the times of concomitant medications are recommended, the actual time of administration should be documented particularly when they differ. Emergency medications such as epinephrine and diphenhydramine should be available in the area where the patients will receive the LMB-2 infusion for treatment of an allergic reaction. Emergency equipment including oxygen should be available in the patient's room.

I.V. Fluid: Patients will receive fluid prophylaxis, consisting of 1000 ml of D5/0.45% NaCl over 2-4 hours prior to LMB-2 and another 1000 ml of D5/0.45% NaCl over 2-4 hours after the LMB-2 infusion is completed. (This is approximately the same amount of IVF given to the last 4 patients on the phase I protocol. However, it is in a more simple administration format). Once the first dose of each cycle is given, patients will receive normal saline, at least 40 cc/hr until day 5-8 when not receiving another type of I.V. fluid.

4.2.1 Vital signs of inpatients will be obtained at the beginning of infusion, at 15 minutes, & at the end of infusion, then every 60 minutes for 2 hours, then as per unit routine. Daily orthostatic blood pressure, weights, I/Os, and physical exam will be done. Daily orthostatic blood pressure will be measured after having the patient in supine and standing position for at least 2 minutes. If standing SBP decreases from supine SBP by > 20 mmHg, then another standing blood pressure measurement will be done at least 3 minutes after the first. Please see section [4.8](#) for management of hypotension. Vital signs of outpatients will be obtained at the beginning of infusion, at 15 minutes, & at the end of infusion, then every 60 minutes for 2 hours. Patients will be monitored for peripheral edema and orthostatic hypotension at least daily. Daily weights will also be recorded. Please see section [4.8](#) for management of hypotension. Determination of DLT

DLT is defined as LMB-2-related grade III-V toxicity, with exceptions below.

4.2.2 Definition of VLS

Definition of Vascular Leak Syndrome (as stipulated by CTEP to be utilized until December 31, 2010): As specified by CTC 3.0, grade II VLS includes symptoms of fluid retention; this protocol further defines that if weight gain is the only feature of VLS in a patient, it should be grade I-II to be classified as grade II VLS. If a patient requires more than an hour's worth of hydration at 20 ml/Kg/hour for hypotension, then the patient will be considered to have grade III hypotension. Grade III hypotension in temporal association with VLS will be considered also as grade III VLS. VLS resulting in respiratory compromise is considered grade III according to CTC 3.0. Respiratory compromise is defined as symptomatic pulmonary edema requiring oxygen or > 10% decrease in oxygen saturation.

Definition of Capillary Leak Syndrome (as stipulated by CTEP) to be utilized after January 1, 2011: As specified by CTCAE 4.0, grade II CLS is defined as symptomatic; medical intervention is indicated; this protocol further defines that if weight gain is the only feature of CLS in a patient, it will be considered a grade II CLS. If a patient requires more than an hour's worth of hydration of 20 ml/Kg/hour for hypotension, then the patient will be considered to have grade III hypotension. Grade III hypotension in temporal association with CLS will be considered also a grade III CLS. Respiratory compromise in the setting of CLS defined as symptomatic pulmonary edema requiring oxygen or > 10% decrease in oxygen saturation will be considered a grade III CLS. Grade III hypotension or grade III CLS is dose limiting.

4.2.3 Treatment Modifications for Toxicities on Current Cycle

Treatment should not be given on Day 3 or 5 until the laboratory values are reviewed for creatinine, AST, ALT, and GGT to determine if treatment modifications are necessary.

Grades I and II Allergic Reaction/hypersensitivity (including drug fever):

- Drug fever only: give acetaminophen every 4-6 hours until resolved (see section 4.8).
- Rash (under Allergic reaction in CTC 3.0 to be utilized until December 31, 2010 and under Skin and Subcutaneous Tissue Disorder in CTCAE 4.0 to be utilized after January 1, 2011): follow guidelines in section 4.8 and hold treatment (up to 3 days) until symptoms resolve.

Grade II Creatinine: Drug will be held (up to 3 days) until Creatinine is \leq Grade I.

Grade III Allergic Reaction or Grade II Allergic Reaction with asymptomatic bronchospasm or urticaria: Stop treatment. Off treatment (DLT).

Other grade III toxicities except for AST, ALT, GGT, and hematologic: Stop treatment. Cycle ends (DLT).

Grade IV toxicities except for grade 4 hematologic toxicity lasting \leq 5 days: Stop treatment. Off treatment (DLT).

Grade IV hematologic toxicity lasting $>$ 5 days except for alopecia: Off treatment (DTL).

Grade IV CPK associated with any other DLT or not resolving to $<$ grade II within 2 weeks: Off treatment (DLT).

4.2.4 Treatment Modifications for Toxicities on Previous Cycle

Retreatment:

- All drug-related non-preexisting toxicities should recover to \leq Grade I prior to retreatment except AST, ALT, GGT, must recover to \leq Grade II.

- Patients who entered the study with \geq Grade II baseline (abnormal) hematological values should have recovered to baseline values prior to treatment.

Dose reduction if at least 1 of the following occurred:

- Grade III toxicities except for AST, ALT, GGT, fever, and hematologic.
- 2nd or 3rd dose held >3 days (due to toxicity)
- Grade II creatinine

4.2.5 Dose Reductions:

- The 1st dose reduction is to 30 $\mu\text{g}/\text{Kg}$ QOD x 3.
- The 2nd dose reduction is to 20 $\mu\text{g}/\text{Kg}$ QOD x 3.
- If a 3rd dose reduction is required, patient is off treatment.
- There will be no dose re-escalation.

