6 DOSING DELAYS/DOSE MODIFICATION

6.1 NO DLT

Continue treatment or retreatment at same dosage.

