6.2 DLT

This also applies to patients undergoing retreatment cycles.

6.2.1 Off Treatment for DLT from:

- Grade III Allergic Reaction and grade II urticaria despite premedication.
- Grade IV toxicity other than hematologic and CPK.
- Grade IV hematologic toxicity lasting > 5 days.
- Grade IV CPK associated with any other DLT or not resolving to < grade II within 2 weeks.

6.2.2 Requiring dose reduction if retreating after DLT from:

- Grade III toxicities except for AST, ALT, GGT, and hematologic.
- Grade IV CPK not associated with any other DLT and resolving to < grade II within 2 weeks.

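### Sections 4.2.4 and 6 give opposite next-cycle dosing rules for grade III fever and for grade II creatinine, with related gaps for grade IV CPK and allergy, and no clause says which section prevails

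*Combined protocol and SAP*

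**What the plan says.** **DLT.** Section 4.2 (Determination of DLT) states: "DLT is defined as LMB-2-related grade III-V toxicity, with exceptions below".

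**Current cycle (4.2.3).** Grade III toxicities other than AST, ALT, GGT and hematologic end the cycle as a DLT; fever is not exempted. For creatinine: "Grade II Creatinine: Drug will be held (up to 3 days) until Creatinine is" grade I or lower, with no DLT label. A general grade IV line takes the patient off treatment and exempts only short hematologic toxicity. A separate CPK line takes the patient off only if another DLT is present or the elevation does not resolve in time. For allergy: "Grade III Allergic Reaction or Grade II Allergic Reaction with asymptomatic bronchospasm or urticaria: Stop treatment", followed by off treatment.

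**Next cycle (4.2.4 and 4.2.5).** Reduction triggers are "Grade III toxicities except for AST, ALT, GGT, fever, and hematologic", a second or third dose held more than 3 days for toxicity, and grade II creatinine. The steps are 40 to 30 to 20 µg/Kg. There is no re-escalation, and a third required reduction means off treatment.

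**Removal (4.9.1, repeated in 6.2.1).** Grade IV toxicity other than hematologic and CPK leads to removal. So does "Grade III Allergic Reaction and grade II urticaria despite premedication".

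**Section 6.** With no DLT (6.1): "Continue treatment or retreatment at same dosage". After a DLT, 6.2.2 requires a reduction for "Grade III toxicities except for AST, ALT, GGT, and hematologic" and for "Grade IV CPK not associated with any other DLT and resolving to < grade II within 2 weeks". Section 6.2 says that it also covers retreatment cycles.

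**The concern.** Sections 4.2.4 and 6 both set the dose at retreatment. Where they differ, two investigators following the protocol faithfully can give the same patient different doses, and neither has deviated. At stake are patient safety with a toxic agent and uniform delivery of the regimen that section 15.2 sets out to test.

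The disputed events are foreseeable. Section 10.1.2.2 lists fever and CK elevation among the grade III-IV toxicities of earlier trials, and increased creatinine among those of grade I-II. Section 2.5 reports one patient with CTCL who had a grade IV CPK elevation without other evidence of DLT. None of these passages gives a rate that could be applied to this trial.

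**Working it through.** No statistical figure is involved, so the check is a side-by-side reading followed by the dose arithmetic.

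| Event | 4.2.3, current cycle | 4.2.4, next cycle | 4.9.1 and 6.2.1, removal | 6.1 or 6.2.2, next cycle |
|---|---|---|---|---|
| Grade III fever | Cycle ends, DLT | Exempt from reduction | Not listed | Reduction (6.2.2) |
| Grade II creatinine | Hold up to 3 days | Reduction | Not listed | Same dose (6.1) |
| Grade IV CPK, isolated and resolving | Off (general line); not off (CPK line) | Not listed | CPK exempted | Reduction (6.2.2) |
| Grade II allergic reaction with urticaria | Off | Not applicable | Off, but with different trigger wording | Not applicable |

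**Fever.** 4.2.4 and 6.2.2 are the same rule for the same decision and differ by one exempted toxicity. The line in 4.2.3 decides whether the current cycle ends, which is a separate question. The conflict is 4.2.4 against 6.2.2.

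**Creatinine.** 4.2.3 (hold now) and 4.2.4 (reduce next time) follow one another and do not conflict. Grade II is below grade III-V, and the creatinine line in 4.2.3 is not labelled a DLT, so 6.1 applies. The conflict is 4.2.4 against 6.1. Absence from 6.2.2 proves nothing, because that list covers only retreatment after a DLT.

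**Direction.** 4.2.4 is the more permissive text for fever and the stricter one for creatinine. Declaring one section to be generally the cautious one would therefore not describe the pattern.

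**Size, using the steps in 4.2.5 and three infusions per cycle:**
- Patient at 40: 3 × 40 = 120 µg/Kg per cycle against 3 × 30 = 90. The difference is (120 − 90)/120 = 25%.
- Patient already at 30: 90 against 3 × 20 = 60. The difference is 30/90 = 33%.
- Patient already at 20: 3 × 20 = 60 against off treatment.

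As an extreme case, suppose the same event occurs in three cycles and nothing else triggers a change. For fever, 6.2.2 gives 30, then 20, then off treatment, while 4.2.4 gives 40 throughout. For creatinine, 4.2.4 gives 30, 20 and off, while 6.1 gives 40 throughout.

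**CPK.** Only 6.2.2 calls for a reduced dose. 4.9.1, 6.2.1 and the CPK line of 4.2.3 do not remove the patient and say nothing about dose, and 4.2.4 does not list the event.

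**Allergy.** 4.2.3 joins its triggers with an or and includes asymptomatic bronchospasm. 4.9.1 and 6.2.1 use an and, add a condition about premedication, and omit bronchospasm.

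**The case against.** **CPK.** A reader might infer that 4.2.3 removes every patient with grade IV CPK. The documents do not support that: the separate CPK line would then have no function, so it is best read as overriding the general line. On that reading 4.2.3, 4.9.1 and 6.2.1 agree on removal. What stands is that 6.2.2 requires a reduction missing from the list in 4.2.4, and that the general line lacks the exemption.

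**Reading the lists together.** One could treat 4.2.4 and 6.2.2 as cumulative, so that a trigger in either applies. This settles CPK, where 4.2.4 is merely silent. It does not settle fever, because it would cancel an express exemption, or creatinine, because 6.1 positively calls for the same dose.

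**Fever through the held-dose trigger.** If fever ends a cycle before the third infusion, the missed dose might count as held more than 3 days, and 4.2.4 would then also reduce. That would narrow the conflict but not remove it: fever after the third infusion is untouched, and 4.2.4 does not say that an omitted dose counts as held.

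**Allergy.** A reader might infer that the dose differs here too. It does not: every version leads to off treatment. If the and merely joins two reasons for removal, the urticaria rules nearly coincide, because hydroxyzine and ranitidine accompany every infusion (4.2). The missing bronchospasm trigger and the literal ambiguity remain.

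**Frequency and endpoint.** A reader might take Table 2 as evidence that these events are common at 40 µg/Kg. The fevers there are all grade 1 or 2, and its creatinine row is merged with proteinuria, so neither disputed event can be counted. A reader might also infer that the response rate or the two-stage design is compromised. The documents give no number of affected patients and no dose-response relation from which to show that, and the Simon boundaries do not depend on these rules.

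**Conclusion.** The point holds as an internal contradiction. Grade III fever (4.2.4 against 6.2.2) and grade II creatinine (4.2.4 against 6.1) are direct conflicts. Each is worth 25% of the next cycle's dose from the starting level and can affect removal through the limit on reductions. Isolated, resolving grade IV CPK is a gap between the two reduction lists plus a loosely drafted general line. The allergy text is a lesser wording point.

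The 25% assumes a patient at 40 µg/Kg with no other reduction trigger in the cycle. The conclusion also assumes that no text elsewhere sets precedence, and none was found in the protocol as provided. The documents do not show which rule is intended. The passages need reconciling because they govern the dosing and stopping of a toxic agent; the case does not rest on any demonstrated effect on the primary endpoint.

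**What to change.** Replace the overlapping rules with one table whose columns are: toxicity and grade; action in the current cycle; action in the next cycle; off treatment or not. Have 4.2.3, 4.2.4, 4.9.1 and section 6 refer to it instead of restating the rules. The table needs explicit rows for grade III fever, grade II creatinine, grade IV CPK (isolated and resolving, or otherwise), and allergic reaction with its bronchospasm and urticaria triggers. The clinical team must decide which rule stands in each row; none is proposed here. The cost is a wording amendment with the usual IRB review, and no added procedures, visits or patients.

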4.3 PHARMACOKINETIC STUDIES

4.3.1 Analysis of LMB-2 in the plasma

Blood samples will be drawn by the patient care unit registered nurse at the times outlined below. Tubes must be labeled with the patient's name, medical record number, date of birth, date, time drawn, and time related to LMB-2 dose. Samples drawn from central venous catheters may be used as long as it is flushed with 5ml of 0.9% sodium chloride prior to obtaining the 2 minute post-infusion sample. Samples of 2 ml of blood will be drawn in a 6 ml sodium heparin tube (green top). Samples of 2 ml blood in serum separator tubes will be drawn with each green top tube to allow ELISA assays to be run on stored serum samples. Tubes of blood collected at the clinical research center (including both inpatient and outpatient units) should be stored upright in the "[name]" container in the designated refrigerator for this purpose. These samples will be collected daily Monday through Friday and taken to our lab for analysis.

4.3.1.1 Days 1 and 5

Inpatients: Pre-dose, 2 minutes after the end of the LMB-2 30-minute infusion, then at 1, 2, 4, 8, and 24 hours.

Outpatients: Pre-dose, 2 minutes after the end of the LMB-2 30-minute infusion, then at 1, 2, and 24 hours.

4.3.1.2 Day 3

Pre-dose, 2 minutes after the end of the LMB-2 30-minute infusion, then at 24 hours.

The acceptable error for PK time points is $+\text{-} 2$ minutes for 2 minute sample; $+\text{-} 15$ minutes for other samples. PK time points are recommended, and if the actual time point differs, the actual time of sample collection should be clearly written on the tube.

4.3.2 Analysis of neutralizing antibodies & soluble Tac

At least 2 ml of blood will be drawn in a Serum Separator Tube (SST) prior to starting each cycle and between days 17-25 of each cycle. Tubes must be labeled with the patient's name, medical record number, date of birth, date, and time drawn. Tubes of blood collected at the clinical research center should be stored upright in the "[name]" container in a designated refrigerator. These samples will be collected daily Monday through Friday and taken to our lab for analysis. Tubes of blood collected outside of the clinical center should be sent by Fed Ex to: [name]. — NIH/SS1 Leidos Biomedical Research, Inc., [name] — [contact].

The presence of antibodies to LMB-2 is determined by a bioassay performed in a CLIA-certified lab in Frederick. In a 96-well U-bottom plate, serum from patients, or 0.2% human serum albumin in PBS (HSA-PBS), is mixed with different concentrations of LMB-2 which are diluted in HSA-PBS. After mixing with serum, the serum-toxin mixtures each contain 90% serum and either 0, 40, 200 or 1000 ng/ml of LMB-2. These mixtures are incubated at 37C for 15 minutes and diluted into cell culture media (DMEM+10% FBS) in a U-bottom 96-well plate so that the final toxin concentrations are 0, 0.16, 0.8, or 4 ng/ml. In triplicate, 50 ul aliquots of these diluted serum-toxin mixtures are added to 150 ul aliquots of SP2-Tac cells (40,000/well in DMEM+10% FBS) in 96-well flat-bottom plates. After incubating the cells for 16-20 hours at 37C, the cells are pulsed for 4-5 hours with $\{\text{³H}\}$ -leucine, harvested, and counted to determine inhibition of protein synthesis. Percent neutralization is calculated by determining the % inhibition of protein synthesis of toxin in HSA-PBS, minus the % inhibition in serum, divided by the % inhibition in HSA-PBS, multiplied by 100. For example, if the 1000 ng/ml concentration of LMB-2 + HSA-PBS caused 75% inhibition of SP2/Tac cells and this concentration in serum caused 50% inhibition, the % Neutralization would be 33%.

